## 5.7 Sample storage

### 5.7.1 Storage of DBSs, RDTs and microscopy slides

All RDTs and microscopy slides from consenting suspected malaria cases, labelled only with survey ID, should be stored in gas-impermeable plastic bags until the survey and data analysis are complete. This is in case they are needed to resolve data inconsistencies or for additional DNA material. **Once the survey report has been completed, these items should be discarded.**

The DBSs on filter paper, labelled with survey ID and tick box or label (No LTS (long-term storage) or No BB (biobanking)), should be stored in a gas-impermeable plastic bag with the same label and with the desiccant taken from the RDT package at ambient temperature in the health facility until they are transported to the central reference laboratory. There, they will be sorted for onward molecular (including DNA sequencing) +/- serological analysis at a qualified participating laboratory (contact malaria\[contact] for links to specific laboratories). After the survey results have been analysed and reported, any unused DBSs or blood or DNA remaining on DBSs after molecular testing and immunoassays should be discarded, **unless patient consent/assent was granted**. For long-term storage, DBSs should ideally be frozen at -20 °C to -70 °C.

### 5.7.2 Long-term storage of DBSs: biobanking

As *pfhrp2/3* gene deletions are an emerging issue, little is known about the etiology, trends and associated genetic mutations that may confer survival advantages or disadvantages. New tools are needed to detect these deleted parasites, and the availability of *pfhrp2/3*-deleted parasite material could accelerate product development and evaluation. For these reasons, the biological materials collected during the survey could be used to advance future research and therefore consent for long-term storage/ biobanking of leftover biological materials is requested.

At the time of consent, all patients will be given an information sheet that is labelled with a unique survey ID and contact information for the study principal investigator and the

national malaria reference laboratory. They can contact these individuals to request removal of their materials from the biobank. If they lose their information sheet and unique survey ID, their samples can be traced only by the principal investigator, who maintains password-protected access to the signed consent forms and corresponding survey IDs.

Long-term storage requires that those coordinating the survey indicate how they envisage the materials being used in the future; to whom the materials will be entrusted (e.g. the Ministry of Health, research institute) and how confidentiality will be maintained; how the quality of the materials will be controlled; how the donor's authorization can be retracted; and under what circumstances donors may need to be re-contacted. These requirements are laid out in Guideline 11 of the *International ethical guidelines for health-related research involving humans* (32).

## 5.8 Data storage and management

Survey case report forms and survey tally sheets do not include any unique/identifiable information. Patient names are only included on consent and assent forms and will be kept in a locked area during and after the study; only the enrolling clinician, study coordinator and principal investigator will ever have access. Electronic data should be password-protected and double-entered at a provincial- or central-level facility. Software will be used for data management and analysis, using coding guides for all study variables.

Once double data entries have been compared and any errors reconciled, data will be cleaned on an ongoing basis. All data will be collected using unique identification numbers linking the epidemiological and laboratory data and maintained in secure, password-protected files. During the survey, and at the central coordinating centre, all paper records collected should be stored in a secure location under lock and key.

The data are broadly classified as individual patient data, malaria infection data, laboratory data and consent data. Other than on the consent form, there should be no possibility to link survey IDs to patient names or any unique identifying characteristics. Encryption will be required for all tablets or electronic data capture devices used for data collection purposes. Permission will be required for data reuse. On-site data managers and their assistants should be trained in all data entry and management processes, and their training logs should be maintained and archived for data quality assurance checks.

All health provider staff at survey sites should participate in training on the conduct of survey data collection. Personnel should be trained in the importance of maintaining consistency in the patient recruitment and data collection protocols and procedures.

The quality assurance approach will focus on providing support for the selection of survey subjects and survey sites, data collection, and management procedures. Data verification techniques will include logic, range and consistency checks. Data validation will be implemented via electronic data entry mechanisms, such as input masks, conditional logic and validation rules. Surveillance personnel should be trained on the rationale and importance of the data verification and validation processes, using specific examples to describe potential implications for the study results. Intermediate statistical analyses will serve as detective and corrective controls by identifying changes in enrolment rates, protocol deviations, duplication of data entry values, or incorrect data values. These results should be communicated to all key personnel on a weekly basis for as long as the cross-sectional data collection is under way. Keeping both paper and electronic data will also serve as a secondary check for the accuracy of data.

## 5.9 Laboratory analyses

### 5.9.1 RDTs

RDTs should be performed according to the manufacturers' instructions for use.

### 5.9.2 Molecular characterization

Molecular characterization should be conducted at a laboratory that has experience in malaria molecular and/or serological techniques and subscribes to the WHO external quality assessment scheme for malaria nucleic acid amplification testing (WHO malaria NAAT EQA scheme) (33) or other scheme for malaria molecular methods. Quantitative PCR is preferred over non-quantitative nucleic acid amplification methods, especially if parasite density is not being measured by microscopy.

The methods proposed by Cheng *et al.* (4) have been used in many previous studies, but there are other options depending on the reference laboratory.

#### 5.9.2.1 DNA extraction and quality control

Verification of the DNA quality is an important aspect of quality control for detecting gene deletions. If conventional PCR methods are used, an aliquot of the DNA should be used for amplification of single-copy genes, such as *msp1*, *msp2* and *glurp* genes, according to standard published protocols (34). For multiplex quantitative PCR users, amplifications of a single-copy parasite gene and a human gene occur simultaneously with amplifications of *pfhrp2* and *pfhrp3* in one assay as internal controls for DNA quality and DNA extraction efficiency; therefore, no additional controls are required.

#### 5.9.2.2 Molecular species diagnosis

Species-specific PCR, either in separate reactions or in multiplex reactions, should be conducted to detect and confirm *Plasmodium* species, including *P. falciparum*, *P. vivax*, *P. malariae*, *P. ovale* and *P. knowlesi*.

#### 5.9.2.3 Characterization of *pfhrp2* and *pfhrp3* sequences and gene deletions in samples

Suggested primer sequences, PCR conditions and expected amplification product sizes for conventional PCR have been published by Cheng *et al.* (4). One of the limitations of this method is that it is a qualitative method and does not detect gene deletions when *pfhrp2*-deleted parasites are mixed with wild-type parasites in the same sample (especially when it is not the predominant strain). A recent review on methods related to *pfhrp2* deletion surveillance discussed the availability of several new molecular methods and their advantages and limitations (see Table 5 below), including various control requirements for reliable identification of gene deletions (35). Among these new methods, multiplex real-time PCR (22–24) and digital droplet PCR (27) are relevant for obtaining quantitative data and identifying deletions within mixed infections. Ideally, *pfhrp2* and *pfhrp3* genes should be characterized by amplification of two gene segments, namely exon 1 (including the intervening sequences between two exons) and exon 2 (including the intronic region between them). However, there are variations in the methods targeting different parts of the genes. Exon 1 codes for a signal peptide and exon 2 codes for the histidine-alanine-rich repeat region of each protein. PCR assays should include appropriate controls, including DNA from laboratory strains with known deletions, such as DD2 (*pfhrp2*-deleted) and HB3 (*pfhrp3*-deleted). If the *pfhrp2* and/or *pfhrp3* genes cannot be amplified despite good quality of DNA (see section 5.9.2.1), demonstrated by the amplification of other single-copy gene sequences, it suggests that the genes have been deleted. Optionally, in order to further confirm and characterize subtelomeric deletions, the following upstream and downstream flanking genes of

*pfhrp2* and/or *pfhrp3* can be amplified: the HPC230 gene located ~5.5 kb upstream and HSP70 located ~6.5 kb downstream of *pfhrp2*, and the HPC475 gene located ~1.7 kb upstream and ACL located ~4.4 kb downstream of *pfhrp3*.

Optional extra: If the *pfhrp2* gene can be amplified, the sequence of the exon 2 amplicon can be determined and translated into an amino-acid sequence. This will enable the classification of the HRP2 protein as type A, type B or type C/borderline structural group, according to the multiplied number of type 2 and type 7 repeats.

**Table 5. Different PCR assays for detecting *pfhrp2* and *pfhrp3* genes with advantages and limitations (adapted from (35))**

Advantages	Limitations
Conventional PCR	

 
• Can be performed in most molecular laboratories and is widely used in many countries
 
• Can detect deletions of both exons
 
• Can identify deletions of flanking genes
 
	
 
• Time consuming at > 2 hours per reaction and qualitative method requiring visualization of PCR products on agarose gels
 
• Requires multiple different PCR reactions; > 6 reactions per sample for control and pfhrp2/3 genes and high volume of DNA needed
 
• Nested PCR and higher chances of contamination
 
• Cannot detect gene deletions when gene-deleted and non-deleted parasites are mixed in the same sample
 

Multiplex real-time PCR	

 
• Streamlined workflow with short turnaround time
 
• Quantitative read-out
 
• Can detect mixed infections with gene-deleted and non-deleted strains
 
• Different target genes are multiplexed in a single reaction, requiring less volume of DNA
 
	
 
• Requires multichannel real-time PCR machine
 
• Training is required for proper interpretation of results
 
• Careful optimization required for individual laboratories
 
• May not detect some partial gene deletions involving one exon, as most assays target one exon only
 

Digital droplet PCR	

 
• Higher confidence deletion calls than with other molecular methods
 
• Can clearly detect mixed infections with gene-deleted and non-deleted strains
 
	
 
• Requires specialized equipment that is not widely available
 
• Requires advanced laboratory and analysis expertise and training
 
• More expensive than conventional approaches
 

Sequencing approaches	

 
• The exact chromosomal location and fragment size of deletions, as well as sequence changes that change codons or affect HRP2/3 expressions, can be mapped
 
• Amplicon-based and whole-genome-based next-generation sequencing methods can be used for parasite population structure and relatedness
 
• Complexity of infection and evolutionary analysis are possible when appropriately sampled data are generated
 
	
 
• More suitable for research studies than for routine programmatic use, as it is expensive and requires advanced laboratory infrastructure and bioinformatics analysis support
 
• Current approaches are not well suited for initial deletion identification, especially in lower parasite density samples
 

### 5.9.3 Serology

From DBSs, ultra-sensitive HRP2 and pLDH detection by multiplex bead immunoassay or enzyme-linked immunosorbent assay (ELISA) may be used to support genotyping results and particularly to resolve discordance between RDT and PCR results.

## 5.10 Data analysis procedures

Following double data entry (see section 5.8) and reconciliation of any errors, the prevalence of false-negative HRP2 RDT results (diagnostic-based) that are suspected to be caused by *pfhrp2/3* gene deletions (output 2) will be determined at the domain/provincial level, with 95% CIs estimated for all point estimates.

Domain-level estimates of output 2 will then be disaggregated by age group, sex, village and recent antimalarial treatment to see whether any patterns emerge. Differences between point estimates across sociodemographic or other collected variables can be investigated using  $X_2$  and/or logistic regressions, as desired. This process should follow the tabulation format in the “dummy” table provided (Annex 8).

After completing the laboratory analyses, once the true number of cases of false-negative HRP2 immunoassay results caused by *pfhrp2/3* deletions is known based on molecular analysis, the prevalence of false-negative HRP2-based RDT results due to *pfhrp2/3* gene deletions based on genotyping +/- serology will be estimated among the confirmed *P. falciparum* cases (main output indicator 1), with 95% CIs for all point estimates, using software package DRpower, accessible via an interactive web app (<https://shiny.dide.ic.ac.uk/DRpower-app/>). This is based on the formula:

$$\text{Proportion of } P. \text{ falciparum} \text{ cases with false-negative HRP2 RDT results due to } pfhrp2/3 \text{ deletions} = \frac{\text{\# of confirmed } P. \text{ falciparum} \text{ cases with } pfhrp2/3 \text{ gene deletions and HRP2-RDT negative results}}{\text{\# of confirmed } P. \text{ falciparum} \text{ cases (positive by either Pf-LDH RDT or microscopy)}}$$

The main output indicator 1 can be disaggregated by domain, age group, sex, village and recent antimalarial treatment to see whether any patterns emerge. Differences between point estimates across sociodemographic or other collected variables can be investigated using  $X_2$  and/or logistic regressions, as desired. This process should follow the tabulation format in the “dummy” table provided (Annex 8).

In addition, the prevalence of *pfhrp2/3* gene deletions based on genotyping +/- serology will be estimated in the cases with suspected *pfhrp2/3* deletions (main output indicator 3) and can be calculated as follows:

$$\text{Proportion of confirmed } P. \text{ falciparum} \text{ cases with } pfhrp2/3 \text{ gene deletions among cases with suspected } pfhrp2/3 \text{ deletions} = \frac{\text{\# of confirmed } P. \text{ falciparum} \text{ cases with } pfhrp2/3 \text{ gene deletions and HRP2-RDT negative results}}{\text{\# of } P. \text{ falciparum} \text{ cases with discordant RDT (HRP2- / Pf-LDH+) or RDT-microscopy (HRP2- / microscopy+) results}}$$

This will indicate the predictive value of false-negative HRP2 RDT results for *pfhrp2/3* gene deletions in different settings.

In addition, the final analysis could include:

- the total number of suspected malaria cases screened;
- the RDT positivity rate per health facility;
- the comparative performance of RDTs and RDT test lines for the detection of *P. falciparum*; and
- a parasite density analysis. This can be used for quality control to ensure that false-negative RDT results were not due to low parasite densities, and to ensure that gene-deleted samples had a high enough parasite density to confirm deletions. Parasite densities can also be used to make comparisons between discordant and concordant samples, and gene-deleted and non-deleted samples.

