Surveillance site	Pre-selected public health facilities representing the spectrum of transmission and geographical diversity across the country
Target population	Individuals meeting the case definition for suspected malaria case
Survey type	Cross-sectional, multi-site
Primary output measures	
 
1. Prevalence of false-negative HRP2 RDT results caused by pfhrp2/3 gene deletions among all symptomatic P. falciparum confirmed cases
 
2. Prevalence of suspected false-negative HRP2 RDT results among symptomatic patients with P. falciparum malaria
 
3. Prevalence of pfhrp2/3 gene deletions among symptomatic P. falciparum patients with a false-negative HRP2 RDT result
 

Secondary output measures (optional)	
 
1. Parasite density, as measured by quantitative PCR and/or microscopy, in patients with suspected false-negative HRP2 RDT results
 
2. Improved understanding of pfhrp2/3 gene deletions, e.g. genetic relatedness and/or drug resistance and fitness, and new and/or improved diagnostic tools for detecting pfhrp2/3-deleted parasites
 
3. Prevalence of parasites with pfhrp2/3 deletions among all symptomatic P. falciparum confirmed cases
 
4. Estimates of the intra-cluster correlation in the prevalence of pfhrp2/3 deletions within sampling domains (e.g. provinces or districts), or other measures of heterogeneity that can help guide future studies
 

Sample size	
A sample size of 300 confirmed P. falciparum cases per sampling domain (30 cases in each of 10 health facilities) is a default proposition to quantify whether or not the prevalence of false-negative RDT results caused by pfhrp2 deletions is above 5%. A sampling domain can be a province, district, state or something else, depending on the administrative boundaries of the country. Once the sample of 300 P. falciparum cases has been enrolled, then molecular confirmation of pfhrp2/3 deletions among suspected false-negative P. falciparum cases should ensue. While 300 confirmed P. falciparum cases is the default sample size, a sample size table is provided to allow for some flexibility. A tool has also been created for customized sample size estimates informed by baseline knowledge and desired power.

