## 5.4 Statistical analysis plan and sample size

The aim of the statistical analysis is to identify survey domains (provinces, districts, states or similar) where there is a high probability that the prevalence of false-negative HRP2 RDT results caused by *pfhrp2* gene deletions is above 5%. Unlike previous versions of the protocol, here, the focus is on identifying areas that are above the threshold (one-tailed test), rather than above or below the threshold (two-tailed test).

Raw data consist of counts of the number of confirmed false-negative HRP2 RDT results caused by *pfhrp2* gene deletions (numerator) and the number of confirmed and enrolled *P. falciparum* cases (denominator) in each health facility. These can be fed into the software package DRpower, accessible via an interactive web app (<https://shiny.dide.ic.ac.uk/DRpower-app/>). This software uses a Bayesian hierarchical model to estimate the prevalence of false-negative HRP2 RDT results caused by *pfhrp2* gene deletions, while accounting for correlations within clusters (for more information on the model, see Annex 3). The software returns a point estimate of the prevalence along with a 95% credible interval (CrI). This information should be presented when summarizing results, but should not be used directly to decide whether a domain is above the threshold. That decision is based on another output of the software: the probability that the prevalence of false-negative HRP2 RDT results caused by *pfhrp2/3* deletions is above 5%. This value is used to categorize study domains as follows:

**Outcome 1:** The posterior probability of being above the 5% threshold is less than 0.95. In this case, there is not sufficient evidence to conclude that the proportion of false-negative HRP2 RDT results caused by *pfhrp2/3* deletions among symptomatic *P. falciparum* patients is greater than 5%.

**Outcome 2:** The posterior probability of being above the 5% threshold is greater than or equal to 0.95. In this case, there is high statistical confidence that the proportion of false-negative HRP2 RDT results caused by *pfhrp2/3* deletions among symptomatic *P. falciparum* patients is greater than 5%.

Programmatic decisions can be made on the basis of these outcomes. Note that it is possible for the CrI to span the 5% threshold when the probability of being above 5% is greater than 0.95 (because the CrI is two-tailed but the statistical test is one-tailed).

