### Power and sample size calculation

Unfortunately, there is no simple formula for statistical power under this model. Instead, a simulation is undertaken as follows:

1. Define the global prevalence of deletions ( $p$ ), the ICC ( $r$ ) and the number of clusters ( $c$ ).
2. Define the per-cluster sample size ( $n$ ) to be the same in all clusters ( $n_i = n$ ).
3. Simulate a data set of deletion counts ( $\mathbf{k}$ ) from the beta-binomial model described above using these values of  $p$ ,  $r$ ,  $c$ ,  $n$ .
4. Analyze this simulated data set using the Bayesian framework above. Determine if the correct conclusion is reached, i.e. that  $p > \mu$  if this is indeed the case.
5. Repeat steps 3–4 many times (typically 1000 or more) to establish the proportion of times the correct conclusion is reached. This is referred to as the **empirical power**.
6. Repeat steps 2–5 over a range of values of  $n$ . Construct an empirical power curve and find the value of  $n$  at which power crosses the target level, typically 80%. This is the minimum sample size  $n_{opt}$  for this parameter combination.
7. Repeat steps 1–6 for a range of parameter combinations to produce sample size tables.

Table 2 in the protocol was produced using this method, assuming a fixed value of  $r = 0.05$ . This value is based on an analysis of historical *pfhrp2/3* deletion studies, in which the mean estimate of the ICC is around this level. Note that the sample size tables produced using this method are only valid if the intention is to analyze data using the DRpower Bayesian model. If the plan is to use a different analysis approach, then a different power and sample size analysis is required.

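### Section 5.10 names chi-square and logistic regression with no allowance for facility clustering; in standard form, comparisons between groups of whole facilities are falsely significant about 21% (two groups) to 42% (five domains) of the time

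*Protocol*

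**What the plan says.** Section 5.4 bases the main analysis on a Bayesian hierarchical model that estimates prevalence "while accounting for correlations within clusters". Annex 3 fixes the ICC at 0.05 for planning, taken from historical deletion studies, and says "Table 2 in the protocol was produced using this method". The default design in section 1 and Table 2 is 10 facilities of 30 confirmed cases per domain, 300 in all.

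Section 5.10 then sets out the descriptive and comparative analyses:

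- Output 2 (suspected false-negative HRP2 results) is determined at domain level, "with 95% CIs estimated for all point estimates". No interval method is named. DRpower is named for output 1 only.
- Output 2 is broken down by age group, sex, village and recent antimalarial treatment. For output 1: "The main output indicator 1 can be disaggregated by domain, age group, sex, village and recent antimalarial treatment to see whether any patterns emerge".
- In both places the comparison method is the same: "Differences between point estimates across sociodemographic or other collected variables can be investigated using" chi-square "and/or logistic regressions, as desired". Neither place mentions a cluster term, a robust variance or a design-based correction.
- Both are to follow the Annex 8 table. Its rows add urban/rural and, optionally, facility, and it has lines for five domains.

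**The concern.** Chi-square and logistic regression in their standard form treat patients as independent. The plan's own sample size rests on the premise that patients at one facility are correlated: Table 2 needs 300 cases with ten facilities but 678 with six.

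The damage depends on the grouping variable. Domain is constant within a facility. Urban/rural is too, if it describes the site or its catchment. For such variables all the between-facility variation enters the comparison, while the standard test counts only binomial variation.

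At stake is the reporting of domain or urban/rural differences that are only facility-to-facility noise. The report goes to the Ministry of Health (section 5.11), and objective 4 concerns predictive value in different settings. The intervals for output 2 raise the same issue and are not optional, because output 2 is a primary indicator. As this is a master protocol, each country that adopts the wording inherits it.

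**Working it through.** **Inputs from the protocol.** 10 facilities × 30 cases per domain (section 1, Table 2); ICC 0.05 (Annex 3); prevalence 10% as the power scenario (section 5.4); five domains (lines in the Annex 8 table).

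**Assumed.** A two-sided 5% test level, since none is stated; 5 urban v 5 rural facilities; no true difference between groups.

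**Step 1: reproduce the plan's own figure.** The Annex 3 model was simulated 3,000 times per design: beta-binomial counts, uniform prior on prevalence, Beta(1, 9) prior on the ICC, success if the posterior probability of exceeding 5% is at least 0.95.

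| Design (facilities × cases) | Power in Table 2 | Simulated |
|---|---|---|
| 10 × 30 | 80% | 80.8% |
| 9 × 37 | 80% | 81.0% |
| 8 × 51 | 80% | 81.9% |

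Table 2 reproduces, so the clustering inputs are read correctly.

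**Step 2: design effect.** DE = 1 + (n − 1) × ICC = 1 + 29 × 0.05 = 2.45. The effective sample per domain is 300 / 2.45 ≈ 122.

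**Step 3: true size of the unadjusted test.** For k groups of whole facilities, size = P(χ² on k − 1 df > its 95% point / DE).

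- Two groups: P(χ²₁ > 3.84 / 2.45) = 21.05%.
- Five groups: P(χ²₄ > 9.49 / 2.45) = 42.35%.

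**Step 4: check by simulation** (40,000 beta-binomial runs, Pearson chi-square, ICC 0.05).

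| Comparison | Prevalence 10% | Prevalence 5% |
|---|---|---|
| Two domains | 21.1% | 20.8% |
| Urban v rural, 5 v 5 facilities | 20.9% | 20.4% |
| Five domains | 42.5% | 41.8% |

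**Step 5: sensitivity to the ICC and the design** (formula of step 3).

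| ICC | Cases per facility | DE | Two groups | Five groups |
|---|---|---|---|---|
| 0.02 | 30 | 1.58 | 12% | 20% |
| 0.05 | 30 | 2.45 | 21% | 42% |
| 0.10 | 30 | 3.90 | 32% | 66% |
| 0.05 | 113 (six facilities) | 6.60 | 45% | 84% |

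**Step 6: factors that vary within a facility** (ICC 0.05, prevalence 10%). A factor balanced within each facility, such as sex, gives about 4%. A factor whose share varies between facilities (assumed SD 0.15), such as recent treatment, gives about 6%. These stay near the nominal 5%.

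**Step 7: output 2 interval.** A simple binomial interval is too narrow by √2.45 = 1.57, about 1.6. At 10% prevalence the half-width would be 1.96 × √(0.10 × 0.90 / 300) = 3.4 percentage points, against 3.4 × 1.57 = 5.3 points allowing for clustering. This carries the ICC of 0.05 over from deletions to suspected false negatives, which is an assumption.

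**The case against.** The case against is substantial, and several parts stand.

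- **The tests are optional and exploratory.** They may be run as desired, with no hypothesis and no level set. This stands and lowers the severity.
- **No formal decision rests on them.** A reader might infer that the decision to change tests is compromised. The documents do not support that: the 5% threshold decision comes from the DRpower posterior probability for each domain, and section 5.6 prioritises a switch by prevalence, not by a p-value.
- **The text is silent on adjustment; it does not rule it out.** A Rao-Scott test is a chi-square test, and a mixed logistic model is a logistic regression. True, so the figures hold only if the named methods are run in their standard form. But section 5.10 names DRpower for output 1 prevalence and names the tests without any qualifier, so the standard form is the natural reading.
- **Few of the named comparisons are affected.** A reader might extend the 21–42% to every row of Annex 8. Age, sex and recent treatment are little affected. No village figure can be given, because village sizes and their nesting in facilities are not stated. A comparison of the named facilities with one another is not inflated, since Annex 3 takes counts as binomial given each facility's own prevalence. Domain is listed for output 1 only; urban/rural appears only in Annex 8.
- **Output 3 should not be swept in.** Its denominator is discordant cases only. If 10% of cases were discordant (an assumption), that is about 3 per facility and a design effect of 1 + 2 × 0.05 = 1.10.

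What remains is narrower but sound: for groups made of whole facilities, the named methods conflict with the correlation that sections 5.4 and Annex 3 plan for.

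**Conclusion.** The point holds for two things: comparisons between groups made of whole facilities, and the output 2 domain intervals. Severity is moderate.

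At the plan's own ICC and cluster size, a nominal 5% test has a true size of about 21% for two such groups and about 42% for five domains. The range is 12% and 20% at ICC 0.02, and 32% and 66% at ICC 0.10. A simple binomial interval for output 2 would be about 1.6 times too narrow.

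The test figures rest on the standard form of the tests, an assumed two-sided 5% level, equal true prevalence and, for urban/rural, an assumed 5 v 5 split of facilities. The interval figure rests on the deletion ICC also applying to output 2.

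**What to change.** In both places in section 5.10, state that comparisons across domain, urban/rural, village or any other grouping that follows facilities use a Rao-Scott chi-square, or logistic regression with a facility random effect, or GEE clustered on facility with a small-sample correction.

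For output 2, name a cluster-aware method for the domain-level 95% intervals, such as the beta-binomial model already used for output 1. Its ICC prior comes from deletion studies, so its use for suspected false negatives should be stated as an assumption.

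The cost is a wording change and slightly more analysis work, with no new data or samples. Intervals will be wider and p-values larger.
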